The study was reviewed and approved by the Institutional Review Board of Stanford University Medical Center. The research is being conducted in the Department of Psychiatry and Behavioral Sciences and is carefully monitored (protocol # 31390) by a Data Safety Monitoring Board at Stanford University. This is a randomized double-blinded placebo-controlled crossover trial totaling 34 weeks in length with ongoing enrollment of adults with BED (up to n = 15) and BN (up to n= 15). Patients are randomized to identical appearing placebo or Qsymia with 4 standard FDA-approved doses of phentermine/topiramate ER: 3.75mg/23mg; 7.5mg/46mg; 11.25mg/69 mg; and 15mg/92mg. The oral administration follows a weekly titration increase as follows: The four doses of Qsymia are titrated in a gradual fashion weekly over the course of four weeks, beginning with the lowest standard dose of phentermine/topiramate (3.75 mg/23 mg) up to the highest standard dose (15mg/92 mg) as tolerated. Each week of the 4-week ramp up period, the dose is increased to the next standard dose, provided no major side effects are reported. The final dose prescribed will be the minimum dose at which effects are seen and side effects are tolerable. Patients are randomized to 12 weeks of treatment with Qsymia or placebo, then a 2-week washout followed by a crossover of 12 weeks (total 26 weeks) and a final 8 weeks of follow-up while off medications, totaling 34 weeks (Figure 1). The washout period of two weeks was chosen to account for sufficient time to allow completion of at least five half lives, given a halflife in plasma of twenty hours for phentermine and sixty-five hours for topiramate. Per the protocol, subjects will be expected to attend 12 study visits spaced 2-4 weeks apart. Compensation in the form of giftcards of twenty US dollars will be given for completion of each assessment: post-treatment 1, post-treatment 2, follow-up 1 and 2 assessments. For participants who complete all four assessments, an additional twenty US dollars will be given.

Sample Size and Statistical Power

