This RCT crossover study is designed to test for a clinically meaningful difference in number of binge days (primary study outcome) when comparing drug to placebo. Assuming a standard paired t-test we estimated that for 80% power, a significance level of 0.05, and a standardized treatment effect size of 0.6 a total of 24 subjects are required. The standardized treatment effect of 0.6 was estimated based on previous studies of topiramate. ^{43, 27} To account for an estimated drop out rate of 20%, the minimum sample size requirement was inflated accordingly to 30 subjects. The paired t-test requires differences to be normally distributed. Should the differences be substantially non-normal, the t-test would no longer be the optimal test with respect to power and the estimated sample size would be slightly conservative."

Randomization Procedure

Eligible participants are randomly assigned to medication group 1 or 2; a cross-over protocol follows the first phase of the trial. This is to be done by randomization as they are sequentially

determined to be eligible for the study. Eating disorder diagnoses (BN and BED) are being recruited and randomized separately to ensure even distribution of diagnoses in each medication group. Five blocks of six permutation identifications were created and a treatment group assigned to each ID. Each treatment group will be shuffled within each block using the RAND function in Excel (Microsoft). This schedule and randomization was determined by the study research coordinator and reviewed by a statistician prior to study initiation.

Participants: Inclusion/Exclusion Criteria

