Measures include demographic data, vital signs (including heart rate, blood pressure, weight), Eating Disorder Examination (EDE),⁴⁵ Eating Disorder Examination Questionnaire (EDE-Q),⁴⁶ Yale-Brown Obsessive Compulsive Scale for Binge Eating (YBOCS-BE),⁴⁷ Three Factor Eating Questionnaire (TFEQ),⁴⁸ Yale Food Addiction Scale (YFAS), ⁴⁹ Binge Eating Scale (BES),⁵⁰ and Patient Health Questionnaire (PHQ-9). ⁵¹ Major assessment points are scheduled prior to randomization (baseline 1), after 12 weeks of treatment (post-treatment 1), prior to the crossover (baseline 2), after the 12 week crossover (post-treatment 2), and after follow-up months 1 (follow-up 1) and 2 (follow-up 2). In addition, vital signs are recorded at each of the 12 medication visits. Weekly online binge trackers are used to record participants' self-reported binge and/or purge episodes.

The primary and secondary study efficacy outcomes are listed in Table 1.

Table 1. Finnary and secondary study enfeacy outcomes
Primary study outcome
Number of binge eating days per week from EDE (average over 28 days)
Secondary study outcomes
Number of binge eating episodes from EDE (average per 28 days)
Abstinence (no binge eating episodes) from EDE over past 28 days
Binge Eating Scale (BES)
Patient Health Questionnaire (PHQ-9)
Eating Disorder Examination Questionnaire (EDE-Q)
Dietary restraint subscale
Eating concern subscale
Weight concern subscale
Shape concern subscale
Global Score for all subscales
Three-Factor Eating Questionnaire (TFEQ)
Cognitive restraint of eating subscale
Disinhibition score subscale
Hunger score subscale
Yale-Brown Obsessive Compulsive Scale modified for binge eating (YBOCS-BE)
Yale Food Addiction Scale (YFAS)

Table 1. Primary and secondary study efficacy outcomes

Data Analysis Plan

The primary outcome measure will be the average number of binge eating days per week, as assessed by the EDE. Secondary outcome measures include the average number of binge eating episodes and percentage abstinence from binge eating. Throughout the study, weekly online binge trackers are used to record participants' binge and/or purge episodes per week per patient report. Vitals (weight, heart rate, blood pressure) and side effects will be assessed at each visit to ensure safety. See Table 2. In addition, any treatment-emergent adverse events will be recorded.

Table 2. Assessment Schedule

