Measures	Baseline1 (Wk0)	Med Visit 1 (Wk0)	Med Visit 2 (Wk2)	Med Visit 3 (Wk4)	Med Visit 4 (Wk8)	Med Visit 5 PT1 (Wk12)	Med Visit 6 BL2 (Wk14)	Med Visit 7 (Wk16)	Med Visit 8 (Wk18)	Med Visit 9 (Wk22)	Med Visit 10 PT2 (Wk26)	Follow Up Med Visit 11 (Wk30)	Follow Up Med Visit 12 (Wk34)
Informed Consent	Х												
Demographics	Х												
Vitals (Weight/HR/BP) & Side Effects	х	Х	Х	Х	Х	Х	Х	X	Х	Х	Х	X	Х
EDE	Х					Х	Х				Х		
BES	Х					Х	Х				Х		
PHQ-9	Х					Х	Х				Х		
EDE-Q	Х					Х	Х				Х		

Study Protocol And Rationale Phentermine-Topiramate ER

TFEQ	Х			Х	Х		Х	
YBOCS-BE	Х			Х	Х		Х	
YFAS	Х			Х	Х		Х	

*Abbreviation Key: Eating Disorder Examination (EDE), Binge Eating Scale (BES), Patient Health Questionnaire (PHQ-9), Eating Disorder Examination Questionnaire (EDE-Q), Three Factor Eating Questionnaire (TFEQ), Yale-Brown Obsessive Compulsive Scale for Binge Eating (YBOCS-BE), and Yale Food Addiction (YFAS), Baseline Assessment (BL1, BL2), Post-Treatment Assessment (PT1, PT2). Crossover occurs at Medication Visit 6 with twoweek washout prior.

Primary and secondary study outcomes will be compared using intention-to-treat (ITT) analysis for all randomized patients. Mixed-effects models with fixed effects for treatment, follow-up period, treatment by period (interaction representing carry-over effect), and eating disorder diagnosis (used to stratify randomization) will be used to estimate the treatment effect. Mixedeffects models include subject-level random effects to account for repeated measurements within subjects. Non-significant treatment by period interaction ($p \ge 0.05$) will be removed from the model before estimating the final treatment effect. In the case of a significant treatment by period interaction (p < 0.05) the analysis will revert to that of a standard parallel arm randomized trial using data from the first period only. A p-value of less than 0.05 is considered statistically significant and the Kenward-Roger degrees of freedom approximation will be used in tests of significance from mixed models.

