Where appropriate normal mixed-effects models will be used to analyze continuous study outcomes, otherwise data will be transformed (e.g. log [value + 1]) or alternatively analyzed using methods appropriate for non-normal continuous data (e.g. log-normal). Outcomes that are binary, categorical or count data will be analyzed using appropriate mixed-effects models (e.g. logistic, multinomial or Poisson). While patients are stratified by eating disorder and it is anticipated subject characteristics by treatment sequence allocation will be balanced within strata, we will conduct secondary analyses adjusting for important baseline covariates (e.g. gender), sample size permitting. Secondary analyses will also include using compliance as a covariate in addition to the total drug received as an exposure. Finally, additional analysis will assess the sensitivity of findings to the missing at random assumption associated with using mixed models according to assumed worst and best-case scenarios.

Discussion

While current treatments for BED and BN are helpful for many, a substantial proportion of patients with BN or BED do not experience symptomatic improvement with current psychotherapy or pharmacotherapy treatments. Therefore, new treatment options are needed. One such option involves repurposing Qsymia (phentermine/topiramate ER), which has been FDA-approved for the treatment of obesity. Topiramate, one of the components of Qsymia, has shown efficacy in reducing disordered eating in both BED and BN. However, its utility has been limited by side effects, which have led to high dropout rates, especially at higher doses.

The described protocol highlights the background and rationale for the first randomized clinical trial to test the use of Qsymia (phentermine/topiramate ER) to treat BED and BN. Phentermine/topiramate ER is an example of a dual combination agent which, due to opposing side effect profiles and pharmacokinetics, may potentially improve efficacy and/or reduce side effects. This may result in lowered doses and less discontinuation for BED and BN compared to monotherapy.

Given that this is the first RCT to use phentermine/topiramate ER in this population (patients

Study Protocol And Rationale Phentermine-Topiramate ER

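### The first-period fallback, and the carry-over test that triggers it, leave out the baseline EDE value already collected before randomization

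*Combined protocol and SAP*

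**What the plan says.** The Data Analysis Plan lists the terms of the primary model: "Mixed-effects models with fixed effects for treatment, follow-up period, treatment by period (interaction representing carry-over effect), and eating disorder diagnosis", with subject-level random effects. An interaction with p ≥ 0.05 is dropped. If p < 0.05, "the analysis will revert to that of a standard parallel arm randomized trial using data from the first period only". No covariate is named for that fallback.

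Baseline adjustment appears only later in the same section: "we will conduct secondary analyses adjusting for important baseline covariates (e.g. gender), sample size permitting". Baseline EDE is not mentioned there.

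The value is nevertheless available. Under Measures, "Major assessment points are scheduled prior to randomization (baseline 1"), and Table 2 marks the EDE at BL1 (week 0), post-treatment 1 (PT1, week 12), baseline 2 (BL2, week 14) and post-treatment 2 (PT2, week 26). Table 1 defines the primary outcome as "Number of binge eating days per week from EDE (average over 28 days"). The plan does not name which of these visits are responses, and it gives neither BL1 nor BL2 a role in the analysis.

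**The concern.** A crossover needs little help from a baseline covariate, because each subject is compared with himself or herself. Two parts of this plan lose that protection. The treatment-by-period test is a between-subject comparison of the two sequences. The fallback is a between-subject comparison of the two arms in period 1, with at most 15 per arm. Both carry the full between-subject variance, which a pre-randomization measurement of the same quantity would reduce.

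The fallback is a prespecified route to the primary result and its least precise one. The plan is silent on covariates there, so whether to adjust, and for what, could be settled after the data are seen.

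**Working it through.** **Inputs from the documents.** Two-period crossover, 1:1, 30 subjects planned (15 per sequence), 24 evaluable after 20% dropout; standardized effect 0.6; alpha 0.05; 28-day outcome window; treatment ends at week 12 and BL2 is at week 14.

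**Assumptions.** The documents give no correlation between EDE assessments. A common r among BL1, PT1 and PT2 is taken as 0.3, 0.5 or 0.7, with normal data, unit variance and no diagnosis term.

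**1. The plan's own figure.** The sizing section begins "Assuming a standard paired t-test we estimated that for 80% power". A two-sided paired t-test with d = 0.6 gives power 0.785 at n = 23 and 0.804 at n = 24. Then 24/0.8 = 30. Both stated numbers reproduce.

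**2. Fallback estimate.** Adjusting for BL1 multiplies the residual variance by 1 − r², so the standard error is multiplied by √(1 − r²).

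| r | 1 − r² | SE multiplier | SE reduction |
|---|---|---|---|
| 0.3 | 0.91 | 0.954 | 5% |
| 0.5 | 0.75 | 0.866 | 13% |
| 0.7 | 0.51 | 0.714 | 29% |

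Simulation with the slope estimated gives slightly less, about 3% to 27% across this range. At r = 0.5, 15 per arm act like 15/0.75 = 20.

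**3. Carry-over test.** This compares the sequences on PT1 + PT2. The variance of the sum is 2(1 + r), and BL1 removes (2r)² = 4r². The variance ratio is [2(1 + r) − 4r²] / [2(1 + r)]:
- r = 0.3: 2.24/2.60 = 0.862, so the SE falls 7%
- r = 0.5: 2.00/3.00 = 0.667, so the SE falls 18%
- r = 0.7: 1.44/3.40 = 0.424, so the SE falls 35%

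**4. Main crossover estimate.** BL1 is the same in both periods and cancels from PT1 − PT2, so complete pairs gain nothing. With 12 complete and 3 PT1-only subjects per sequence (the 20% dropout), generalized least squares gives SE 0.2316 to 0.2307, 0.1980 to 0.1961 and 0.1552 to 0.1526, falls of 0.4%, 1.0% and 1.7%.

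**5. Power.** Taken alone, a period-1 comparison with 15 per arm and d = 0.6 in level SD has power 0.355 without BL1 and 0.383 / 0.448 / 0.602 with it (noncentral t). These figures ignore the fact that the fallback is used only after a significant pretest. Simulating the whole two-stage rule at 15 per sequence gives:
- No carry-over: the fallback triggers about 5% of the time. Overall power goes from 0.753 to 0.751, 0.870 to 0.869 and 0.960 to 0.961. Given that the fallback triggered, rejection is 0.50–0.54 without BL1 and 0.48–0.53 with it.
- Carry-over of 25% or 50% of the drug effect: overall power changes by at most 0.008.
- Carry-over of 100%: overall power rises by about 1 to 5 points.
- Root mean square error of the fallback estimate, given that it triggered and with no carry-over, falls by about 4% to 33%.

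**6. Type I error of the two-stage rule.** Without BL1: 0.068 / 0.073 / 0.075. With BL1: 0.066 / 0.068 / 0.068. A second simulation gave 0.069 / 0.075 / 0.080 and 0.068 / 0.073 / 0.072.

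**7. Why BL1 and not BL2.** The Table 2 footnote says "Crossover occurs at Medication Visit 6 with twoweek washout prior". A 28-day window ending at week 14 starts at week 10, and period-1 treatment runs to week 12, so 14 of 28 days (50%) are on period-1 drug or placebo. The washout was set on elimination: "The washout period of two weeks was chosen to account for sufficient time to allow completion of at least five half lives". For topiramate, 5 × 65 h = 325 h = 13.5 days, which fits in two weeks but does not clear the outcome window.

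**The case against.** The strongest reply is that little changes in the procedure the trial will run. Subjects are their own controls, BL1 cancels from the main contrast, the fallback is seldom reached, and overall power barely moves. **This stands.** A reader might infer from the nominal fallback powers in step 5 that the trial gains 3 to 25 points of power. It does not, because those powers are not conditional on the pretest. A reader might also infer that the primary crossover estimate is biased or inefficient for want of a baseline term. Step 4 shows otherwise.

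Second, the plan does not propose using BL2. **This also stands.** If BL2 were used as a change-score baseline, and the drug effect ended at once at washout, the estimate would be about 1.25 times the true effect. A reader might take that as a bias in this plan, but nothing in the documents describes that analysis. Treating PT1 and PT2 as the responses is the natural reading, given the paired t-test sizing, and it is unbiased.

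Third, the secondary analyses could include baseline EDE. **This stands only in part.** They do not name it, they depend on sample size, and they leave the fallback and its trigger unadjusted.

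Fourth, r is assumed, equal correlations and normality may be optimistic for a bounded measure, and diagnosis may already absorb part of what BL1 explains. **This is fair.** At r = 0.3 the gain is small.

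**Conclusion.** The point holds as a matter of precision and prespecification in one branch of the plan. The fallback and the test that leads to it omit a covariate that is already scheduled. Using it would narrow the fallback estimate's standard error by about 5% to 29% and the carry-over test's by about 7% to 35% over r = 0.3 to 0.7, without raising type I error.

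The documents do not support more than that. No bias is claimed in the analysis as written, and overall power is essentially unchanged unless carry-over approaches the size of the drug effect. Nor does the covariate cure the inflated error of the test-then-revert rule, which is a separate matter. The remark on BL2 is a clarification only.

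Confidence is medium. The facts are plain in the text, but the size of the gain rests on an assumed correlation. The change is worth making because it costs almost nothing.

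**What to change.** Add to the Data Analysis Plan:

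*For EDE outcomes, PT1 (week 12) and PT2 (week 26) are the two responses per subject. For the primary outcome, BL1 EDE binge days per week, on the same scale as the response (for example log[value + 1] if that transformation is used), is the single baseline covariate in both the mixed model and the first-period fallback. The 28-day BL2 EDE value is descriptive only and is neither a period-2 baseline nor a response.*

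Gender and other covariates can remain in the secondary analyses. The cost is three sentences and one degree of freedom. Sample size, visits, washout and data collection do not change.

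### Diagnosis stratifies the randomisation but enters the crossover model only as a main effect, which leaves the within-patient treatment estimate essentially unchanged; a diagnosis-by-period term would be a cheap safeguard (minor)

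*Combined protocol and SAP*

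**What the plan says.** Under Randomization Procedure, the two diagnoses are recruited and randomised separately. Under Data Analysis Plan, the mixed model has fixed effects for treatment, period and treatment-by-period, "and eating disorder diagnosis (used to stratify randomization) will be used to estimate the treatment effect", with subject-level random effects. A treatment-by-period term that is not significant is removed; if it is significant, only first-period data are used. All randomised patients are analysed. No diagnosis-by-period term is listed.

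The same section adds that "we will conduct secondary analyses adjusting for important baseline covariates (e.g. gender), sample size permitting". It also plans analyses using compliance and total drug received, and logistic, multinomial or Poisson mixed models for outcomes that are not continuous.

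Under Sample Size and Statistical Power, the trial is sized for "80% power, a significance level of 0.05, and a standardized treatment effect size of 0.6", on the basis of a paired t-test: "a total of 24 subjects are required", then "inflated accordingly to 30 subjects" for 20% dropout.

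**The concern.** In a two-period crossover the treatment effect is estimated from each patient's difference between periods, compared between the two sequences. Anything fixed within a patient drops out of that difference. A diagnosis main effect therefore does not bring the stratification into the treatment estimate. To do that, diagnosis must be allowed to shift the period difference, and that is a diagnosis-by-period term.

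Two things are at stake. First, if BED and BN change differently from period 1 to period 2, that variation stays in the residual even though stratified randomisation has largely balanced it between sequences. The standard error is then too wide and power is lost. Second, a secondary linear analysis adjusted for gender as a main effect has almost no capacity to differ from the primary one, so a reader could take its agreement for more support than it gives.

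**Working it through.** **The plan's own figure.** Inputs from Sample Size and Statistical Power: power 80%, alpha 0.05, effect 0.6, taken as mean over SD of the within-patient difference. Sidedness is not stated; two-sided is assumed because it reproduces the 24. The normal approximation gives (1.960 + 0.842)² / 0.6² = 21.8. The exact noncentral-t calculation gives power 78.5% at n = 23 and 80.4% at n = 24, so 24. Dropout: 24 / 0.8 = 30. Both figures reproduce.

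**Why the main effect cancels.** For patient i in period j, write

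y_ij = mean + period_j + τ·treatment_ij + diagnosis_i + b_i + e_ij.

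The within-patient difference is

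D_i = y_i1 − y_i2 = (period_1 − period_2) ± τ + (e_i1 − e_i2),

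with + for drug first and − for placebo first. Diagnosis and the random effect b_i are gone, and gender would go the same way. The estimate of τ is half the difference in mean D between sequences. With 12 patients per sequence and SD(D) = 1, its SE is ½·√(1/12 + 1/12) = 0.204, whether or not diagnosis is in the model.

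**Check by fitting.** Random-intercept REML fits used 30 simulated patients, assumed within-patient correlations of 0.3 to 0.7, and 300 simulations per setting. Shifts are in SDs of D.

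- Complete pairs: adding diagnosis or gender moved the treatment estimate by 0.0000 in every simulation; mean SE ratio 0.999 to 1.000.
- 20% lost before period 2: adding diagnosis moved the estimate by 0.011 to 0.020 on average (largest 0.07 to 0.12), SE ratio 0.991 to 0.999. Adding gender moved it by 0.006 to 0.011 on average (largest about 0.07), SE ratio about 1.00. The treatment SE itself is about 0.18 to 0.20.

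**What is lost if period effects differ.** Let g be the BED–BN difference in period effect, in SDs of D. The documents give no value, so a range is shown. Take 24 pairs with diagnosis balanced across sequences. With the main effect only (22 residual df), each patient's D carries ±g/2 that is not modelled, which adds 24·g²/4 to the residual sum of squares. The SE is inflated by about √[(22 + 24g²/4)/22]; for g = 1.0 that is √(28/22) = 1.128. With diagnosis-by-period the extra term is removed and 21 df remain.

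| g (assumed) | SE inflation | Type I error, main effect only | Power, main effect only | Power, with diagnosis-by-period |
|---|---|---|---|---|
| 0 | 1.000 | 5.0% | 80.2% | 80.0% |
| 0.25 | 1.008 | 4.8% | 79.7% | 80.0% |
| 0.5 | 1.034 | 4.3% | 78.3% | 80.0% |
| 1.0 | 1.128 | 2.8% | 72.3% | 80.0% |
| 1.5 | 1.270 | 1.4% | 62.2% | 80.0% |

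With the added term, type I error is 5.0% throughout. Other simulation runs gave 4.2% to 4.4% at g = 0.5 and 2.8% to 2.9% at g = 1.0. Kenward-Roger degrees of freedom were approximated by residual degrees of freedom.

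In mixed-model fits with 30 randomised, six of them with period 1 only, and g = 1.0, the mean SE was 0.221 with the diagnosis main effect or with no covariate, and 0.199 with diagnosis-by-period.

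**Where the main effect does work.** The treatment-by-period test and the first-period fallback are between-patient comparisons. If BED and BN differ in outcome level by 1 SD of D (assumed), including diagnosis cuts the SE of the carry-over term to 0.82 to 0.93 of its unadjusted value, and the fallback SE to about 0.89 (at correlation 0.5).

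**The case against.** The strongest reply is that the loss depends on an effect the documents nowhere report. The Discussion names learning and carry-over as general hazards of a crossover; it does not say they differ between BED and BN. With no difference, the planned test has its nominal level and 80% power. At 0.5 SD the loss is about 2 points, and the 1.0 SD case needs a gap 1.0/0.6 = 1.67 times the treatment effect the trial is sized for. All of this stands, and it is why the point is minor.

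A reader might also infer three stronger things that the documents do not support:

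- *That the diagnosis term is useless.* It sharpens the carry-over test, which decides which estimate is reported, and the first-period fallback.
- *That the adjusted analyses must match the primary one.* Exact invariance needs complete pairs and a linear model. The plan analyses all randomised patients with 20% dropout expected, and uses non-linear mixed models for some outcomes. Compliance and total drug received can differ between a patient's two periods and can move the estimate.
- *That the plan rules out a better adjustment.* It does not fix the form of the covariate analysis, and a second baseline is collected before crossover, so period-specific baselines remain possible.

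Finally, a period interaction for every secondary covariate is not clearly cheap with about 24 pairs. The Introduction puts women at roughly 90% of BN cases, so gender-by-period could rest on very few men. The plan already makes covariate adjustment conditional on sample size.

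What survives is the cancellation itself, and the fact that the plan randomises by diagnosis without letting diagnosis act on the contrast it tests.

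**Conclusion.** The point holds as a minor one about efficiency and interpretation. In the final linear crossover model, diagnosis and gender main effects leave the treatment estimate and its SE unchanged in complete pairs, and essentially unchanged with 20% dropout. Agreement between the primary and a gender-adjusted linear analysis is therefore weak evidence of robustness.

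Any loss of power is conditional: none if BED and BN share the same period effect, about 2 points at 0.5 SD, about 8 points at 1.0 SD. These figures assume 24 complete pairs, an effect of 0.6, two-sided 0.05, and diagnosis balanced across sequences. With 15 patients per diagnosis, an odd number, balance can only be approximate.

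It would be wrong to conclude that the primary result is biased or its false-positive rate inflated: in every case examined, type I error is at or below 5%. The point concerns the precision of the single pooled effect and does not address whether the drug works differently in BED and BN.

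**What to change.** Before unblinding, add a diagnosis-by-period term to the primary mixed model, keeping treatment, period and diagnosis, and state that it stays whatever its p-value. The diagnosis main effect should also stay in the carry-over test and the first-period fallback. The cost is one sentence and one degree of freedom: if period effects do not differ, power goes from 80.2% (22 df) to 80.0% (21 df). The 24 evaluable and 30 randomised are unchanged.

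For the secondary adjusted analyses, enter a patient-level covariate such as gender together with its period interaction only where there are enough patients in each category. Where there are not, report the main-effect version if wanted, but say that it can hardly differ from the primary analysis and do not cite its agreement as robustness.

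### The primary analysis chooses between both periods and the first period by a carry-over pre-test, with each branch tested at 0.05, so its false-positive rate is about 7-8% rather than 5%

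*Combined protocol and SAP*

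**What the plan says.** The Data Analysis Plan (text after Table 2) fits mixed models with "fixed effects for treatment, follow-up period, treatment by period (interaction representing carry-over effect), and eating disorder diagnosis", plus a subject random effect and Kenward-Roger degrees of freedom. No baseline score is listed among the terms.

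The interaction then decides which analysis is final:

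- If its p-value is 0.05 or more, the term "will be removed from the model before estimating the final treatment effect", and both periods contribute.
- If it is below 0.05: "In the case of a significant treatment by period interaction (p < 0.05) the analysis will revert to that of a standard parallel arm" trial, using first-period data alone.

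One criterion covers both branches: "A p-value of less than 0.05 is considered statistically significant". Nothing in this section or in Sample Size and Statistical Power adjusts either branch for the preliminary test. The sample size rests on a single paired t-test at 0.05. The Discussion names carry-over and learned effects as a limitation that the analysis will assess, but does not mention the error rate of the two-stage rule.

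**The concern.** A preliminary test harms the final test when the two are correlated, and here one branch is. In a 2x2 crossover the treatment-by-period interaction equals the between-sequence difference in patient totals over the two periods. That quantity is independent of the within-patient treatment contrast, so the two-period branch does no damage. It is strongly correlated with the first-period comparison, because the first-period score is half of each total. If one sequence happens to contain patients who binge more, the pre-test tends to be significant, and so does the first-period comparison it hands over to.

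Two things are at stake. The stated 0.05 level for the primary outcome is not the real one. And a positive result from the fallback would be hard to interpret, since it would come from the branch most prone to false positives and would discard the within-patient contrast on which the trial was sized.

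**Working it through.** **Inputs.** From the documents: pre-test level 0.05; final test level 0.05; 24 evaluable patients, 30 enrolled; 1:1 allocation to sequence (12 or 15 per sequence); model terms as listed above. Assumed: two-sided tests; normal, complete data; compound symmetry; within-patient correlation ρ of 0.3 to 0.7.

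**The plan's own figure.** A two-sided paired t-test with effect size 0.6 has power 80.4% at n = 24 and 78.5% at n = 23. Inflating for dropout, 24/0.8 = 30. Both stated numbers reproduce. A one-sided test would need only 19, so two-sided is the natural reading.

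**Correlation of pre-test and fallback.** With unit variance, Cov(y₁, y₁+y₂) = 1+ρ and Var(y₁+y₂) = 2(1+ρ), so

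corr = (1+ρ)/√[2(1+ρ)] = √[(1+ρ)/2].

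**Large-sample false-positive rate, no drug effect and no carry-over.**

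P(reject) = 0.95 × 0.05 + P(|Z_pre| > 1.96 and |Z_fallback| > 1.96)

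- ρ = 0.3: 0.0475 + 0.0223 = 0.0698
- ρ = 0.5: 0.0475 + 0.0266 = 0.0741
- ρ = 0.7: 0.0475 + 0.0319 = 0.0794

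**Simulation of the full rule** (random-intercept REML with the listed terms including diagnosis; 600,000 null trials per setting):

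| ρ | Correlation | Rule, N = 24 | Rule, N = 30 | Both periods always | P(reject given fallback) |
|---|---|---|---|---|---|
| 0.3 | 0.81 | 6.95% | 6.91% | 5.05% | 0.43-0.44 |
| 0.5 | 0.87 | 7.31% | 7.35% | 4.98-5.00% | 0.52 |
| 0.7 | 0.92 | 7.90% | 7.84% | 4.99-5.03% | 0.62 |

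The fallback fires in about 5% of null trials and then rejects 43-62% of the time, which adds 2.1-3.1 false positives per 100 trials. The two-period branch contributes about 4.75 per 100.

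**Outside the assumptions.**

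- *Correlation:* the rate is about 6.9-7.1% at ρ of 0 to 0.1, where part of the excess comes from holding the subject variance at zero or above, and 8.7% at ρ = 0.9.
- *Baseline 1 as covariate* (not in the stated model): 6.7-7.2% if in both pre-test and fallback; 5.9-6.5% if in the fallback only.
- *Change from each period's baseline* (also not stated): about 7.0-7.1% with the subject variance held non-negative, and 6.3-6.5% with simple t-tests. In the former, always using both periods already gives 5.8-5.9%.
- *Dropout:* 3 of 15 per sequence without period 2 gives 6.8-7.8%.
- *Bounded outcome:* binge days out of 28, raw or log(value + 1), gives 6.3-8.0% over assumed means of 0.8-2.9 days per week and 2-25% zeros.

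Poisson and logistic models were not simulated.

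**How well the pre-test finds carry-over.** Read 0.6 as standardized by the SD of paired differences, so the drug effect is τ = 0.6√[2(1−ρ)]. Let carry-over λ enter period 2 of the drug-first sequence. With n per sequence and λ = τ, the pre-test's expected z is

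τ/√[4(1+ρ)/n] = 0.6√{n(1−ρ)/[2(1+ρ)]}.

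This is 1.21 at n = 15, ρ = 0.3 and 0.62 at n = 12, ρ = 0.7. By simulation the pre-test fires in 9-22% of trials when λ = τ and in 6-9% when λ = τ/2. The sample size section does not say what standardizes 0.6; read as a between-arm difference, the figures are 12-17% and 7-8%.

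**The case against.** The strongest case for the rule has four parts.

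1. *The excess is small and the trial is early-phase.* The excess is 1.9-2.9 points in a 30-patient proof-of-concept study, and the rule is pre-specified and published, so it is not a choice made after seeing data. This stands, and it limits the severity. It does not make the stated 0.05 correct.

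2. *The baseline handling is open.* Adjusting for Baseline 1 could bring the rate as low as 5.9%. However, the model lists no baseline term, and covariate adjustment is placed among the secondary analyses, so the unadjusted reading is the natural one. Every variant tried exceeds 5%.

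3. *The rule guards against carry-over, which the protocol takes seriously.* With carry-over equal to the drug effect, the rule has more power than always using both periods: 34-40% against 29% at 12 per sequence, and 41-48% against 35-36% at 15. Part of that advantage is bought with the inflated level. If the fallback is cut to the level that restores 5% overall (0.0024-0.0031), the difference shrinks to between −0.5 and +1.1 points. If instead the two-period test is given the same inflated level, the difference is about −2 to +6 points. Some advantage may therefore remain under complete carry-over, but mainly at low ρ.

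4. *Always using both periods biases the estimate if carry-over is real.* This stands, and it is the true cost of the fix. Against it, the Methods set a two-week washout to cover five half-lives: 5 × 65 h = 325 h, or 13.5 days, for topiramate, and 5 × 20 h = 100 h for phentermine. That makes pharmacological carry-over less likely, which weakens the case for a pre-test. It does not address learned effects.

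**Conclusion.** The concern holds. As written, the primary test does not keep its 5% level: the rate is about 6.9-7.9% with normal complete data, no carry-over and ρ of 0.3-0.7. The direction is secure, since the rate was above 5% at every correlation tried from 0 to 0.9 and under every baseline, dropout and bounded-outcome variant examined. The decimals depend on the assumed correlation and on the unadjusted reading of the model.

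The rule gives little in return. It usually misses carry-over, even carry-over as large as the drug effect, and when there is none it costs about 1.3-2 points of power. This should be fixed, but given the modest excess and the trial's early phase it does not undermine the design.

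**What to change.** By a dated, justified amendment before unblinding:

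- Delete the pre-test and the reversion to first-period data. Make the two-period mixed model (treatment, period, diagnosis, subject random effect, Kenward-Roger) the primary analysis whatever the interaction shows.
- Report the treatment-by-period estimate with its confidence interval descriptively. This still meets the Discussion's commitment to assess carry-over.
- Give a first-period comparison adjusted for Baseline 1 EDE as a labelled sensitivity analysis.
- State whether and how the Baseline 1 and Baseline 2 EDE scores enter the model. Baseline 2 is taken at week 14, after two weeks of washout, so a 28-day score would include 28 − 14 = 14 days of period 1 treatment.

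**Cost.** No new data or visits are needed, but the plan is published and Trial Status reports recruitment since 2015. The documents do not give the blinding status; if unblinding has already happened, both analyses should be shown and the change disclosed as post hoc.

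Statistically this is a trade-off. The two-period estimate has expectation τ − λ/2, so it is attenuated by 25% when carry-over is half the drug effect and by 50% when it equals it. Relative to the current rule, power falls by 1-3 points and 5.5-12 points in those two cases. The 5% level is restored only when there is no carry-over. If the sponsor prefers to keep the two-stage rule, the fallback would need a level of about 0.0024-0.0031 to hold 5% overall under the assumptions above.
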